### 9.3.2 Assessment of the Relationship of Adverse Events to Study Drug

The Investigator will make a causality assessment about the relationship of each AE to study drug. To ensure consistency of AE and SAE causality assessments, Investigators should apply the following general guideline:

**Not Related:** The AE has an etiology other than the study drug (eg, preexisting medical condition, underlying disease, intercurrent illness, or concomitant medication); and/or the AE has no plausible temporal relationship to administration of the study drug (eg, cancer diagnosed 2 days after first dose of study drug).

**Possibly Related:** An AE that follows a reasonable temporal sequence from administration of the study drug, follows a known or expected response pattern to the study drug, but that could readily have been produced by a number of other factors.

**Probably Related:** An AE that is clearly related to the study drug or its administration (ie, an event that follows a reasonable temporal sequence from administration of the study intervention, follows a known or expected response pattern to the suspected intervention, that is confirmed by improvement on stopping and reappearance of the event on repeated exposure and that could not be reasonably explained by the known characteristics of the subject's clinical state).

**Definitely Related:** The AE is clearly related to the study drug; a re-challenge confirms the association (not required or desirable in some circumstances but provides strong evidence when it happens).

For all AEs and SAEs, Investigators will make separate assessments of causality about the relationship of the event to study drug and to drug administration (ie, IVT injection).

**Note:** The Investigator's assessment of causality for individual AE reports is part of the study documentation process and will be recorded in the subject's medical record, AE eCRF, and SAE form if applicable. Adverse events recorded without the Investigator's assessment of the relationship to study drug will be followed up until causality is assigned.

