#### **9.4.1 Adverse Event Reporting Period**

Any event/condition noted once the subject receives their first dose of study drug in the contralateral eye will be captured as an AE.

In the first treated eye all events/conditions will be captured as an AE as treatment continues from study PQ-110-001.

All AEs and SAEs regardless of attribution will be collected until at least 3 months following the last administration of study drug or the subject's EOS visit, whichever is later. At the last scheduled visit, the Investigator should instruct each subject to report to the Investigator any subsequent AEs/SAEs that the subject's personal physician believes could be related to prior study treatment.

Adverse events and SAEs related to study drug that persist > 3 months after the last study drug dose should be followed until resolution or until they return to baseline, stabilize, the subject is lost to follow-up, or it has been determined that the study drug or participation is not the cause of the AE/SAE.

Resolution of AEs and SAEs (with dates) should be documented on the AE eCRF and SAE form (if applicable) and in the subject's medical record to facilitate source data verification.

For some SAEs, the Sponsor or its designee may follow-up by telephone, facsimile, electronic mail, and/or a monitoring visit to obtain additional case details deemed necessary to appropriately evaluate the SAE report (eg, hospital discharge summary, consultant report, or autopsy report).

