### **9.5 Serious Adverse Events Notification**

For all SAEs, regardless of suspected causality, an SAE form must be completed (or faxed if using paper form) within 24 hours of discovery of the event to:

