#### ***DRUG SAFETY***

***Phone toll-free: See Study Reference Manual for Phone Number***

followed by submission of written case details on an SAE form within 24 hours.

Serious AEs occurring any time after study participation that are considered by the Investigator to be possibly related to study drug must also be reported. The following are important points to remember when completing the SAE form:

- If complete information is not available, at a minimum, subject identifier, suspect drug, study center identifier, event or outcome, and Investigator assessment of causal relationship to study drug should be provided.
- A rationale for the causality assessment of an SAE should always be included, so that a better understanding of the event can be compiled.
- Follow-up information, such as laboratory reports, discharge summaries, autopsy reports, and information concerning outcome of the event should be submitted by revising the SAE form as soon as the information becomes available. Copies of source documents, with subject identifiers redacted, should be submitted only when they are written in English. If source documents are not in English, the Investigator must summarize the source documents, providing a complete English narrative that includes a description of the events as it evolved, the results of all diagnostic procedures performed, treatments administered, and outcome of the event. A query regarding a follow-up report should be answered within 5 working days from receipt of the query.
- Appropriate diagnostic tests and therapeutic measures are to be performed as necessary and reported on the SAE form.
- All SAEs must be reported to the IRB/EC, if applicable. See the International Council for Harmonization (ICH) Good Clinical Practice (GCP) E6, Section 4.11.1 ([ICH GCP 2016](#)).

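### Follow-up of events still open 3 months after the last dose, and reporting of new SAEs after participation, depend on relatedness to study drug alone, although relatedness to the injection is rated separately

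*Protocol*

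**What the plan says.** Section 9.2.1 of the protocol counts complications of intravitreal injection as adverse events. Section 9.3.2 then asks for separate causality assessments, for all AEs and SAEs, of the "relationship of the event to study drug and to drug administration (ie, IVT injection"). SAP Section 4.7.1 keeps the two ratings apart and lists separate tables for each.

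Four rules govern collection, follow-up and reporting:

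- **Collection (9.4.1).** "All AEs and SAEs regardless of attribution will be collected until at least 3 months following the last administration of study drug" or the End of Study (EOS) visit, whichever is later.
- **Follow-up of open events (9.4.1).** The events to be followed beyond 3 months after the last dose are "Adverse events and SAEs related to study drug that persist" past that point. Follow-up runs to resolution, return to baseline, stabilisation or loss to follow-up, or stops once "it has been determined that the study drug or participation is not the cause of the AE/SAE".
- **SAEs in general (9.5).** "For all SAEs, regardless of suspected causality, an SAE form must be completed". Follow-up information "should be submitted by revising the SAE form as soon as the information becomes available".
- **SAEs after participation (9.5).** Those "occurring any time after study participation that are considered by the Investigator to be possibly related to study drug must also be reported".

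**The concern.** The two ratings allow an event to be recorded as not related to the drug but related to the injection. Such an event falls outside the follow-up rule in 9.4.1 and outside the rule in 9.5 on SAEs after participation, because both name the drug only.

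The route of administration is part of what this study evaluates. The primary objective (Section 3.1) is long-term safety and tolerability of the product given by intravitreal injection, and injections are repeated in each eye. Read literally, the protocol follows a drug-related event open at EOS to its end. It lets an injection-only event stop at its last recorded status, for example a pressure rise left as not recovered (an illustration; the documents report no such case). SAP Section 4.7.1 tabulates outcomes including not resolved, so the asymmetry would carry through to the report.

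**Working it through.** This is mainly a comparison of texts. The plan gives no figure to reproduce.

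**Which rule covers an event rated drug: not related, injection: related?**

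| Situation | Governing rule | Condition | Covered? |
|---|---|---|---|
| Any AE up to the later of 3 months after last dose or EOS | 9.4.1, collection | None on attribution | Yes |
| SAE during the study | 9.5, opening rule | None on causality | Yes, with outcome updates through the SAE form |
| Non-serious AE still open more than 3 months after last dose | 9.4.1, follow-up | Related to study drug | No stated duty |
| New SAE after participation | 9.5, later rule | Possibly related to study drug | No stated duty |

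The opening rule of 9.5 does not rescue the last row. If it applied without limit after participation, the separate and narrower rule for that period would be redundant.

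**Does neighbouring text supply the missing condition?**

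- *Relatedness grades (9.3.2).* There are three related grades: possibly, probably and definitely. Only the middle one, "An AE that is clearly related to the study drug or its administration", names administration as a cause, so 1 of 3 does. The threshold used in 9.5 is possibly related, which does not.
- *Exit clause (9.4.1).* It mentions participation as well as drug, but it ends follow-up and does not start it.
- *Instruction to subjects (9.4.1).* Subjects are asked to tell the investigator about later events that their own physician links to prior study treatment. That might include the injection, but it creates no duty to follow an open event or to report to the sponsor.
- *Documentation of resolution (9.4.1).* It says where resolution is recorded, not how long an event is followed.

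**How long is stated follow-up of an injection-only event?**

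Inputs: EOS is 3 months after the subject's last dose (Section 7.3); the eyes are injected 3 months apart, each every 6 months (Section 7.2); at most 11 subjects enrol (Section 5.1).

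- Last-injected eye: final injection to EOS = 3 months.
- Other eye: its final injection is 3 months before the subject's last dose, so 3 + 3 = 6 months to EOS.
- Event first noted *d* months after the subject's last dose: remaining stated follow-up = 3 − *d*. For *d* = 1 this is 2 months; for *d* = 2 it is 1 month.
- Upper bound on who can be affected: 11 subjects × 2 eyes = 22 eyes; one subject is 1/11 = 9.1%.

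The durations assume the standard schedule with both eyes treated and EOS on time. Section 7.2 lets the between-eye interval be adapted, which would change the 6-month figure but not the 3-month one.

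**The case against.** The best reply is that the protocol does not draw the line between drug and injection as sharply as this reading does. One related grade already includes administration, the examples under not related do not mention the injection, and the reference to participation in the exit clause would have little purpose if only drug-caused events were being followed. On that view the intended scope was wider, and investigators would act accordingly. This is fair evidence of intent, but the trigger itself still names the drug alone, next to an instruction to rate the two causes separately.

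The second reply is that little exposure remains. Collection ignores attribution up to at least 3 months, SAEs during the study are reported and updated whatever their cause, and pressure and inflammation are checked on the day of injection and the day after (Section 4.2.1.3). What is left is non-serious injection-only events open after EOS, and new SAEs starting after participation for which the drug is not even a possible cause. This stands as a limit on size. The documents do not show that either kind of event is likely. The 3 months is also a minimum, so sites may follow events for longer, although nothing requires it.

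The third reply is that Section 9.2.4 defines events of special interest partly by route of administration and its list is redacted. Handling rules there could already cover the injection-related events that matter most. This cannot be checked from the public text, and the conclusion is conditional on it.

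Finally, the study is descriptive and single-arm, and no conclusion has been shown to change. That supports treating the point as an inexpensive improvement and not as a flaw in the primary analysis. The counts of 11 subjects and 22 eyes are ceilings, not estimates of lost information.

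**Conclusion.** The concern holds. Section 9.4.1 sets no follow-up duty for an injection-only event still open more than 3 months after the last dose, and Section 9.5 sets no reporting duty for a new injection-only SAE after participation. The surrounding text softens both gaps but closes neither.

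The effect is narrow. Frequency and severity of AEs, the primary endpoint in Section 4.1.1, are intact up to the later of 3 months after the last dose or EOS. The possible loss is the eventual outcome of a few persisting events, mainly non-serious, and any late SAE attributed to the injection alone.

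This rests on a literal reading of the two rules and on the redacted section on events of special interest not already covering these cases. No rate of injection-only events is given, and none is assumed. The wording should be changed; confidence is medium because of the redaction.

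**What to change.** Make three wording changes:

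1. In 9.4.1, start follow-up for events *related to study drug or to its administration (IVT injection)*.
2. In 9.5, require reporting of SAEs after participation that are *possibly related to study drug or to its administration (IVT injection)*.
3. In 9.4.1, align the exit clause to *the study drug, its administration or study participation*.

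If Section 9.2.4 already sets follow-up for injection-related events, add a cross-reference to it in 9.4.1.

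The cost is a wording amendment to two sections, with no new scheduled visits or procedures. The downside is slightly longer follow-up of a few events and possibly a few more late SAE reports, in at most 11 subjects.

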#### **9.4.2 Eliciting Adverse Events**

A consistent methodology of non-directive questioning for eliciting AEs at all subject evaluation time points should be adopted. Examples of non-directive questions include:

*“How have you felt since your last clinic visit?”*

*“Have you had any new or changed health problems since you were last here?”*

Age-appropriate non-directive questions should be employed for eliciting AEs from pediatric subjects. Non-directive questions may also be used to elicit AEs from parents/caregivers of pediatric subjects, at the discretion of the Investigator.

#### **9.4.3 Recording Adverse and Serious Adverse Events**

Investigators should use correct medical terminology/concepts when recording AEs or SAEs on the eCRF and/or SAE form. Colloquialisms and abbreviations should be avoided. Serious AEs must also be recorded on the AE eCRF. Only one medical concept should be recorded in the event field on the AE eCRF and SAE form (if applicable).

##### **9.4.3.1 Adverse Events Occurring Secondary to Other Events**

In general, AEs occurring secondary to other events (eg, cascade events or clinical sequelae) should also be entered as separate AEs. For example, if severe diarrhea is known to have resulted in dehydration, both diarrhea and dehydration should be entered as AEs on the eCRF, and if also serious, on the SAE form.

##### **9.4.3.2 Persistent or Recurrent Adverse Events**

A persistent AE is one that extends continuously, without resolution between subject evaluation time points. Such events should only be recorded once in the eCRF unless their severity

increases. If a persistent AE becomes more severe or occurs more frequently, it should be recorded again on the AE eCRF with the increased severity grading.

A recurrent AE is one that occurs and resolves between subject evaluation time points and subsequently recurs. All recurrent AEs should be recorded individually on the AE eCRF.

#### **9.4.3.3 Abnormal Laboratory Values**

Only clinically significant laboratory abnormalities will be recorded as AEs on the eCRF and SAE form (if applicable).

If the laboratory abnormality can be characterized by a precise clinical term, the clinical term should be recorded as the AE or SAE. For example, an elevated serum potassium level of 7.0 mEq/L should be recorded as “hyperkalemia”.

Observations of the same clinically significant laboratory abnormality from visit to visit should not be repeatedly recorded as AEs on the eCRF and SAE form (if applicable), unless their severity, seriousness, or etiology changes.

#### **9.4.3.4 Deaths**

All deaths that occur during the protocol-specified AE reporting period ([Section 9.4.1](#)), regardless of attribution, will be recorded on the AE eCRF and SAE form and reported to the Sponsor within 24 hours of event knowledge.

When recording a death, the event or condition that caused or contributed to the fatal outcome should be recorded as a single medical concept. For example, if death resulted from respiratory failure, the AE recorded should be “Respiratory Failure”, and the outcome of the AE would be “Death”. If the cause of death is unknown and cannot be ascertained at the time of reporting, record “unexplained death” on the AE eCRF and SAE form.

#### **9.4.3.5 Preexisting Medical Conditions**

A preexisting medical condition is one that is present at the start of the study. Such conditions should be recorded on the Medical and Surgical History eCRF.

A preexisting medical condition should be recorded as an AE or SAE only if the frequency, severity, or character of the condition worsens during the study. When recording such events on an AE eCRF and SAE form (if applicable), it is important to convey the concept that the preexisting condition has changed by including applicable descriptors (eg, “more frequent headaches”).

#### **9.4.3.6 Hospitalization, Prolonged Hospitalization or Surgery**

Any AE that results in hospitalization or prolonged hospitalization should be documented and reported as an SAE unless specifically instructed otherwise in this protocol.

#### **9.4.3.7 Pregnancy**

If a female subject or a female partner of a male subject becomes pregnant while the female subject or the male partner is receiving study drug

a Pregnancy Report form should be completed and faxed to the Drug Safety designee within 24 hours of learning of the pregnancy, using the fax numbers listed in the Study Reference Manual.

Abortion, whether therapeutic or spontaneous, will be reported on a Pregnancy Report form and faxed to the Sponsor according to the instructions in the Study Reference Manual. If the abortion meets seriousness criteria ([Section 9.2.2](#), Serious Adverse Event Definition), this information will be captured on the AE eCRF and SAE form.

Any congenital anomaly/birth defect in a child born to a female subject or to a female partner of a male subject exposed to the study drug should be recorded and reported as an SAE.

#### **9.4.3.8 Overdose Reporting**

Overdoses must be reported to the Sponsor on an AE eCRF and an SAE form for tracking purposes and will be considered a protocol deviation. Overdose is defined as any study drug dose administered above the intended dose. Additional instructions for reporting overdose information will be provided by the Sponsor at the time of notification.

### **9.5 Serious Adverse Events Notification**

For all SAEs, regardless of suspected causality, an SAE form must be completed (or faxed if using paper form) within 24 hours of discovery of the event to:

#### ***DRUG SAFETY***

***Fax toll-free: See Study Reference Manual for Fax Number***

Any fatal or life threatening (ie, imminent risk of death) event that is attributed by the Investigator to the study drug must be *immediately* telephoned to:

#### ***DRUG SAFETY***

***Phone toll-free: See Study Reference Manual for Phone Number***

followed by submission of written case details on an SAE form within 24 hours.

Serious AEs occurring any time after study participation that are considered by the Investigator to be possibly related to study drug must also be reported. The following are important points to remember when completing the SAE form:

- If complete information is not available, at a minimum, subject identifier, suspect drug, study center identifier, event or outcome, and Investigator assessment of causal relationship to study drug should be provided.
- A rationale for the causality assessment of an SAE should always be included, so that a better understanding of the event can be compiled.
- Follow-up information, such as laboratory reports, discharge summaries, autopsy reports, and information concerning outcome of the event should be submitted by revising the SAE form as soon as the information becomes available. Copies of source documents, with subject identifiers redacted, should be submitted only when they are written in English. If source documents are not in English, the Investigator must summarize the source documents, providing a complete English narrative that includes a description of the events as it evolved, the results of all diagnostic procedures performed, treatments administered, and outcome of the event. A query regarding a follow-up report should be answered within 5 working days from receipt of the query.
- Appropriate diagnostic tests and therapeutic measures are to be performed as necessary and reported on the SAE form.
- All SAEs must be reported to the IRB/EC, if applicable. See the International Council for Harmonization (ICH) Good Clinical Practice (GCP) E6, Section 4.11.1 ([ICH GCP 2016](#)).

## **9.6 Expedited Reporting of Suspected Unexpected Serious Adverse Reactions**

- The Sponsor or its designee is responsible for notifying the study centers of all expedited SAEs (ie, 7/15 Day SUSARs) that occur during any clinical studies that are using the study drug. The Sponsor or its designee shall also notify Central ECs and Central IRB of SUSARs or significant risks to subjects, per local requirements. All SUSARs will be reported to the Regulatory Authorities as per local requirements.
- The Investigator will notify local IRB/EC of SUSARs or significant risks to subjects, per local country requirements. The Investigator must keep copies of all AE information, including correspondence with the Sponsor or local IRB/EC on file.
- All studies that are conducted within any European country will comply with the [European Clinical Trial Directive 2005/28/EC](#), the [Clinical Trial Directive 2001/20/EC](#), the [Detailed Guidance CT-3 \(2011/C 172/01\)](#), and [Regulation 536/2014](#).

## **10.0 STATISTICAL METHODOLOGY**

### **10.1 General Considerations**

Analyses will generally be descriptive in nature and will focus on data collected during this study. Baseline functional and structural measurements for the first treated eye will be those from study PQ-110-001. Baseline functional and structural measurements for the contralateral eye will be collected during the Screening visit. The incidence of AEs and changes in clinical laboratory assessments will be summarized for subjects by dose group, age category (pediatrics and adults), and for the study population. Efficacy endpoints will be summarized for all subjects using descriptive statistics for each eye. For all the relevant analyses, the data may be summarized for subjects by dose group, age category, genetic status, and severity of disease (BCVA and other visual function and/or functional vision parameters). An analysis by 3- or 6-month intervals may also be performed. Summary statistics for other safety, efficacy, and PK endpoints will be presented. Further details will be provided in the Statistical Analysis Plan (SAP).

A comprehensive SAP will specify the statistical methodology, and table, listing, and figure (TLF) formats for all aspects of the planned analyses. The SAP supports the completion of the Clinical Study Report (CSR) for this protocol.

All AEs will be considered in determining the safety profile of QR-110 unless obviously unrelated. As an open-label extension study, exploratory analyses not necessarily identified in the SAP may be performed to support the clinical development program. Any p values that will be calculated according to the analysis plan will be interpreted in view of the exploratory nature of the study. Additionally, no adjustment for multiplicity will be done due to the exploratory nature of the study. Any post-hoc, or unplanned, analyses not identified in the SAP will be clearly identified in the CSR, in accordance with applicable Standard Operating Procedures (SOPs) of the Sponsor.

